## **D. Research Design and Methods**

### **D.1 Study Design**

We will conduct a pragmatic stratified randomized controlled trial (RCT) of two interventions using a two-phase stepped-wedge design. We will first evaluate the effect of a single-component intervention (simple audit). Second, we will evaluate the effect of a multicomponent intervention (audit + tailored recommendations + quality improvement collaborative calls combined with Change/Implementation Team support) with considerable external support and a close relationship with the University of California leadership team, but local flexibility. We will also assess whether participation in an in-person meeting (where education in quality improvement is emphasized) enhances the impact of the audit and/or the multicomponent intervention. We will determine if the simple, inexpensive audit and feedback approach is as effective as the intensive, multicomponent intervention at reducing facility-level mean radiation dose or the percentage of examinations with doses above the benchmark compared to baseline. Since audit with feedback is expected to be only weakly effective, we will implement it first. The

second intervention will give tailored feedback on needed changes plus guidance using quality improvement methods that facilitate organizational change.

A total of 116 facilities from one of 20 parent institutions will participate in the trial. The individual facilities will be the unit of comparison in the trial. However, in order to ensure that facilities that are highly integrated with each other (for example, share staff and management) do not get randomized to separate groups (which would be impractical to implement and lead to complete cross over) we assessed the relative independence of each facility so that we can keep interdependent facilities in the same randomized units (which in some cases will include more than one facility). Thus, the unit of comparison is the individual facility, whereas the unit of randomization is the facility cluster (see G below). This resulted in 84 units (facility clusters) to be randomized.

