#### Planned analyses:

##### Primary Analysis

###### 1. Effective dose.

Time frame (see Section M for details):

Baseline 1: 9-12 months prior to simple audit;

Follow-up 1: 3-6 months following 4 weeks washout after simple audit;

Baseline 2: 2-6 months prior to multicomponent intervention;

Follow-up 2: 3-6 months following 2 weeks washout after multicomponent intervention;

Within each anatomic area, the mean effective dose and the proportion of CT scans with an effective dose over the benchmark during the Follow-up period will be compared to doses during the Baseline period. The benchmark for each anatomic area is defined as the 75th percentile of the dose distribution during Baseline 1.

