## **L. Study Arms (Tracks)**

The study will divide facility clusters into three separate tracks. Each facility will first receive the simple audit, followed later by the multicomponent intervention, and will be staggered as to when they begin each intervention. Two of the three randomized tracks will be invited to participate in an in-person meeting, which will be timed to coincide with the audit for one of

the tracks and to coincide with the multicomponent intervention for one of the tracks. The third track will serve as a control (i.e., no in-person meeting). This will permit assessing whether the in-person meeting enhances the impact of the audit and/or multicomponent intervention.

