### **L.1 Audit**

Audits will be sent to each facility summarizing their own doses and comparing them to the other facilities in their randomized track. The audits will be stratified by anatomic area and age group (adult/child) using each of the identified dose metrics. Facilities will be provided dose metrics in comparison to other facilities in their facility cluster, the healthcare institution, and overall compared with other facilities in their track and in the entire study. The audits will summarize data from a time period prior to provision of the audits and multicomponent interventions.

Each audit report will compare the facility against other facilities within their institution and to the other facilities/institutions in the study. The comparison will be made based on mean as well as median radiation doses, and the proportion of examinations above the baseline 75th percentile of radiation dose. Results will be provided both unadjusted and adjusted for patient size (using mid scan diameter as a surrogate for patient size). The audit reports will include descriptive tables and figures showing protocol-specific measures of radiation dose, outcome metrics indicating how their radiation doses rank against other facilities, stratification of results by age and anatomic area and results by the machine make and model. The audits will also provide information on patients who received very high doses.

After facilities receive the initial audit report, there will be a four-week (“washout”) period where facilities will have time to make changes to their imaging processes. For example, facilities can hold staff meetings or make any changes that could lead to dose optimization prior to when we assess their doses the next time. Facility leads will be responsible for developing plans for using audit data for quality improvement with our targeted suggestions; for example, meeting with technologists to review protocols or modifying existing protocols for a particular

anatomical area. This phase will test whether complete, comparative data alone can effect changes in dose levels.

Audit reports will be sent to “facility lead champions” (as requested/noted by the site PI) and facilities will be encouraged to share the information broadly with other contributors to radiologic practices at their facility or institution.

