## **L.2. Multicomponent Intervention**

The multicomponent intervention will, in addition to the audit reports, provide a more detailed, tailored, facility-specific feedback (more detailed audit report) that will match the information provided on the audits to workable interventions and actionable suggestions for lowering doses. For example, not only will high dose protocols be identified, but also facilities will be provided with guidance on technical parameters that they could alter to match the performance of the best performing facilities. Further, the multicomponent intervention will include an invitation to participate in quality improvement collaborative calls where facilities will meet via teleconference regularly (weekly over 8 weeks) to learn about quality improvement and share experiences and challenges with adopting the various practices that we are promoting. These regular meetings between a UCSF established Change Team and a hospital created Implementation Team will help guide the implementation of the key aspects of the intervention.

Facilities will receive recommendations targeted to performance, which will be sent to individuals, identified by the PI at each facility, but will ideally include facility leads, heads of radiology departments, and Implementation Team leaders. Recommendations will focus on specific, alterable, technical factors (e.g., scan length); specific protocols to use more or less frequently (e.g. multiphase protocols); protocol modifications based on cross-facility analyses, etc. Recommendations will be tailored to the facilities practices. The audit reports will be a starting point for discussions about strategies and techniques to improve CT dose levels.

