We will also compare the multicomponent intervention and simple audit effects to determine which is more effective. We will also compare how participation in the in-person meeting impacts the effects of the simple audit and multicomponent intervention by including interactions with an effect of in-person meeting and the particular intervention. Each facility will act as its own control, and we will control for underlying time trends, which are estimable because of the stepped-wedge design.

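### The fixed audit-then-package order does not identify which intervention is more effective, and the planned comparison names no baseline although its answer can depend on that choice

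*Combined protocol and SAP*

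**What the plan says.** Two sentences promise a verdict between the interventions. N.1: "We will also compare the multicomponent intervention and simple audit effects to determine which is more effective". D.1: "We will determine if the simple, inexpensive audit and feedback approach is as effective as the intensive, multicomponent intervention"; that sentence goes on to define effectiveness as reduction in mean dose or in the share above benchmark, relative to baseline.

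The order is the same in all three tracks. Section L: "Each facility will first receive the simple audit, followed later by the multicomponent intervention". D.1 gives the reason: "Since audit with feedback is expected to be only weakly effective, we will implement it first". Randomisation sets when each track starts and when an in-person meeting is offered, not the order.

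The package contains an audit. D.1 defines it as "audit + tailored recommendations + quality improvement collaborative calls combined with Change/Implementation Team support", and L.2 says: "The multicomponent intervention will, in addition to the audit reports, provide a more detailed, tailored, facility-specific feedback".

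The four-week washout after the audit is described in L.1 as a "period where facilities will have time to make changes to their imaging processes". It is time for the audit to take effect, not for its effect to disappear. Section K then sets "Baseline 2: 2-6 months prior to multicomponent intervention", which falls after the audit. N.1 compares post-package doses with both Baseline 1 and Baseline 2 and relies on the stepped-wedge structure to estimate time trends.

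**The concern.** The audit effect is measured from facilities that have received nothing. The package effect is measured either from facilities that have already been audited (Baseline 2) or across the whole sequence (Baseline 1). Against Baseline 2, the package starts from whatever reduction the audit left behind. Against Baseline 1, it is credited with the earlier audit, the repeat audit and a longer exposure. Neither is the effect of the package in audit-naive facilities, which a stand-alone ranking needs.

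The comparison bears on a practical choice between a cheap audit and intensive support. A manager reading that one is more effective, or that the audit is as effective, would take it as a statement about choosing one or the other. The trial has no facilities that show the second option on its own.

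**Working it through.** **The plan's own figure.** No power or effect size is given for this comparison. Section O's 80% power concerns a fall from 25% to 20% above benchmark against baseline, with 84 clusters and 27-28 scans per facility per period. Its formula and number of periods are not stated. A Hussey-Hughes stepped-wedge calculation with three periods and a coefficient of variation of 0.7 gives 0.80-0.81, so the figure is attainable but not uniquely reproducible. It is used below only as a source for an audit effect.

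**What the design identifies.** In percentage points, let
- a = fall from Baseline 1 to Follow-up 1 (audit alone);
- c = audit effect still present at Baseline 2 = r × a, where r is the share retained;
- s = total fall from Baseline 1 to Follow-up 2 (audit then package);
- m = fall the package would produce in audit-naive facilities.

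The data inform a, c and s. The Baseline 2 contrast is s − c and the Baseline 1 contrast is s. A stand-alone head-to-head compares m with a, but no track informs m. Setting m = s assumes that the earlier audit leaves no mark on the level reached after the package, which the trial cannot test.

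**Odds-ratio illustration.** Assumed: audit 25% to 20% (Section O's powered change), fully retained, then 17% after the package.
- Odds: 0.25/0.75 = 0.3333; 0.20/0.80 = 0.25; 0.17/0.83 = 0.2048.
- Audit against Baseline 1: 0.25/0.3333 = 0.75.
- Package against Baseline 2: 0.2048/0.25 = 0.82.
- Package against Baseline 1: 0.2048/0.3333 = 0.61.

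To match the audit's 0.75 from 20%, the odds must reach 0.25 × 0.75 = 0.1875. That is a share of 0.1875/1.1875 = 15.8%, a total fall of 25 − 15.8 = 9.2 points.

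**When the ranking turns.** In points, the audit ranks first on the Baseline 2 contrast when s − r × a < a, that is, s < (1 + r) × a. With a = 5:

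| r | audit ranks first if s is below |
|---|---|
| 0 | 5.0 |
| 0.25 | 6.25 |
| 0.5 | 7.5 |
| 0.75 | 8.75 |
| 1 | 10.0 |

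With s = 8 and r = 1, the Baseline 2 comparison is 5 against 8 − 5 = 3 and the audit ranks first. The Baseline 1 comparison is 5 against 8 and the package ranks first. With s = 12 and r = 1, the package ranks first either way (7 or 12 against 5).

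**Does time-trend adjustment or more data help?** Generalised least squares with period effects and a cluster random intercept was applied to three assumed three-track layouts (6, 10 and 12 periods, 84/3 = 28 clusters per track, coefficients of variation 0.4 and 1.1). With a = 5, s = 8 and r = 1, the estimates stayed at 5.0 for the audit and 3.0 (Baseline 2) or 8.0 (Baseline 1) for the package. At 27.5 scans per facility per period, the 2-point difference on the Baseline 2 contrast has a standard deviation of 1.91 in the 12-period layout. The audit is then ranked first with probability Φ(2/1.91) = 0.85. At 600 scans (60 a day × 30 days / 3 areas, assumed) the standard deviation is 0.41 and the probability is about 1.00. On the Baseline 1 contrast the probabilities are 0.02-0.03 across layouts and about 0. More scans only make the answer for the chosen contrast firmer.

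**The case against.** The other side has a good deal to say.
- The primary objective in C.1 is each intervention against baseline. The head-to-head appears neither in Section C nor in Section K's list of analyses, only in one sentence each of D.1 and N.1.
- D.1's sentence is qualified as relative to baseline, and the package includes an audit by definition. Audit alone against audit plus support, both from Baseline 1, is a fair reading.
- Follow-up 2 against both baselines and Follow-up 1 against Baseline 1 are already planned, so a reader should see more than one contrast.
- Audit-first was a stated choice, and Section O expects the package to have the larger effect.

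All of this stands and limits the point. It does not remove it: N.1 names no baseline for the comparison, and under D.1's more favourable reading the package arm is still two audits and a longer exposure, not the package on its own.

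Three stronger readings are tempting and not supported. A reader might infer that the plan will pick the wrong winner. That needs the Baseline 2 contrast, a decision rule that the plan does not give, and a total effect below the thresholds above. A reader might infer that late audit effects would be counted in full as package effect. N.1 says period lengths differ by intervention and track, so the audit-to-package interval may also differ. Full aliasing would require the late effect to arrive at the package start in every track, and the timeline figure that could show this is not available here. A reader might infer that the trial's main result is compromised. The contrasts of each intervention with its baseline do not depend on the head-to-head.

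**Conclusion.** The point holds in a limited form and should be corrected. The fixed order and the audit inside the package mean that the design does not identify a stand-alone ranking, and calendar-trend control does not separate the package from prior audit exposure. The plan leaves the baseline open, and that choice can decide the answer: 0.82 or 0.61 for the package against 0.75 for the audit in the illustration. Those values are assumptions. Section O's 5-point change is a powered difference, not a predicted audit effect; 17% and full retention were chosen to show the mechanism. A large enough package effect ranks first under either baseline. What the trial can estimate is the added effect of the package after an audit and the total effect of the sequence.

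**What to change.** In N.1 and D.1, replace the two sentences that promise a stand-alone ranking or equality with:

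- (a) the incremental effect of adding the package, including its repeat audit, in facilities already audited: Follow-up 2 against Baseline 2, named as the test of added benefit;
- (b) Follow-up 1 and Follow-up 2 each against Baseline 1, labelled 'audit alone' and 'audit then package'.

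Where the timeline makes Follow-up 1 and Baseline 2 distinct periods, keep them as separate audit-only levels in the model. Report the drift between them beside the package estimate, so that a growing or fading audit effect is visible. Where they overlap, say so and omit the drift.

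The cost is small: wording in two sections and, at most, one extra period level in a model that already includes all periods. No new data or change to randomisation or the interventions is needed. The trial gives up a stand-alone head-to-head claim that its design cannot support.

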## N.2 Mixed methods qualitative and quantitative analyses

The organizational survey includes a combination of quantitative and qualitative questions. We will examine these questions using standard descriptive statistics. We will assess the relationship between facility-level characteristics as assessed through the surveys and dose levels (baselines as well as changes in dose), using responses to our facility surveys using mixed methods approaches. In order to make the analysis more robust we will construct domains using the survey questions. The first step in constructing these "domains" is to use exploratory factor analysis (EFA) to identify groups of questions that simultaneously correlate highly with each other but not to the point of redundancy. We will then combine the questions within each of these groups, or domains, to form composite domain scores (i.e. measures) that will become continuous predictive variables, combined with structural facility-level variables from the first survey and with patient-level variables (e.g. age, size, etc.) for a series of linear models that assess how these facility- and patient-level measures relate to: a) baseline dose levels and b) changes in dose levels after the interventions in our study.

Our final statistical models of dose and changes in dose will use primary (facility-level, scanner-level, and patient-level) analytical variables derived directly from our Radimetrics database, in

combination with facility-level characteristics derived from our two surveys. We will use the same hierarchical modeling approaches as described above to estimate the relationships between our predictors (facility-level, scanner-level, patient-level, and various interventions) and dose measures.

## **O. Sample Size**

Statistical power depends on between-class coefficient of variation (standard deviation between facilities divided by average prevalence per facility). Based on prior research, we expect these values to vary between 0.4 and 1.1, depending on anatomical region and response metric. With 84 unique clusters, reflecting 116 facilities, to be randomized and at least 27-28 scans per facility for each anatomical region and age group (adult/children), in each measurement period, we will have an 80% power to detect a change of 5 percentage points (from 25% to 20%) in percentage of examinations with doses above the benchmark after the intervention versus baseline, using a two-sided significance level of 5%. The exceptions to this are children's head scans, which only require 15 scans per facility in each measurement period to achieve the same power with 84 clusters. We expect each facility to contribute, on average, at least 60 scans per day. With each measurement period being at least 1 month it is very likely 80% power will be surpassed. The effect of multicomponent intervention is expected to be greater than the effect of auditing; thus, the same sample size would also be sufficient in detecting the significance of multicomponent intervention.

## **P. Ethical Considerations and DSMB**

The primary ethical concern for the project relates to loss of confidentiality for the participating facilities and institutions. We will do everything we can to maintain the confidentiality of the facilities. Through the project we may identify individuals who have received exceedingly high radiation exposures. These will be reviewed with the Data Safety Monitoring Board (DSMB) to determine what course of action, if any, is necessary. We will be interviewing staff at many of our facilities. Potentially they might disclose views that could be perceived as negative by their

peers or supervisors. All of the survey results will be kept confidential and will not be reported back to the individual facilities so that the results cannot be linked to an individual or even to a facility or institution.

## **R. APPENDICES**

### **R.1. Variable List - Survey**

#### **Facility-Level Variables**

##### Organization Location

Geographic location (U.S., non U.S.; Geographic region of the U.S.)

Population size of community where facility located

##### Organization Structure

Services provided (hospital/inpatient, emergency, ambulatory, other)

##### Type of Facility

Academic/Teaching Hospital

Trauma Center (Level 1, 2, or 3)

Public Hospital

Community Hospital

Private Hospital

Acute Care Facility

Primary Cancer Facility

Pediatric Hospital

Tertiary Referral Hospital

Outpatient Imaging Facility

##### Payer mix

Racial and ethnic breakdown of patients

##### Staffing and Capacity

Number of radiologists

Number of technologists

Number of CT machines

Number of medical physicists

##### CT Protocols (instructions)

Number by anatomic area

Who establishes them, who can modify them

Manufacturer (protocols pre-set on machines)

Organizational leadership

Medical Physicist (one for the org.)

Medical Physicist (at the particular hospital)

Radiology site

Lead radiologists

Any individual radiologists

Head Technologist

Technologist performing exams

Other

Are protocols locked

How often are protocols reviewed and updated

Facility Practice Sharing

Activities focused on optimization

Status of ongoing efforts on optimization

## **R.2. Variable List – Dose Registry Variables**

### **Patient-Level Variables**

Sex

Age

Size (mid scan diameter)

Indication for imaging (derived)

### **CT examination-level variables (each examination/encounter may include 1 or more radiating events/ imaging acquisitions)**

Time of examination (date, day of the week, time of the day)

Machine (make, model)

Study description

Protocol name

Scan region(s):

Dose parameters of each imaging acquisition

Average mAs

Average kVp

Scan length

Pitch

Collimation

Scan thickness

CTDIvol for each imaging acquisition

DLP for each imaging acquisition

Effective Dose for each imaging acquisition

CTDIvol (average, weighted by scan length) for each examination

DLP (sum) for each examination

Effective Dose (sum) for each examination

**R.3 Parental Organizational Survey (pdf attached)**

**R.4 Sublevel Organizational Survey (pdf attached)**

**R.5 Implementation Survey (pdf attached)**

**R.6 Timeline (pdf attached)**
